### **7.11.2 Clinical Laboratory Evaluations**

{Not applicable. Not a routine procedure in the protocol}.

### **7.11.3 Vital Signs**

Vital signs are collected during the scheduled physical examinations. Heart rate, body temperature, height, and weight will be summarized descriptively at each scheduled visit. The change from baseline to each scheduled post-baseline visit will also be presented. Measurement parameters will be sorted alphabetically

### **7.11.4 12-Lead ECGs**

{Not Applicable. Not a routine procedure in the protocol}

### **7.11.5 Other Observations Related to Safety**

{Not applicable}

## **7.12 Interim Analysis**

Interim analyses are planned in this study: Day 57 for Cohort 1 and Day 140 for Cohort 2 (primary analysis time point). The Day 57 interim for Cohort 1 will be provided initially for Groups 1 and 2, which will complete Day 57 substantially earlier than Groups 2a and 3. The Day 57 IA for Groups 2a and 3 combined will be provided at a later time. Thus, the Day 57 IA will be conducted in two parts to be followed by the Day 140 IA in Group 4. Interim analyses will be finalized after the primary safety and immunogenicity data for the group are available, ie, after all subjects from Cohort 1 have completed Day 57 or terminated early and after all subjects from Cohort 2 have completed Day 140 or terminated early.

The interim analyses will be performed by a separate group of unblinded statisticians and programmers at Quintiles who will have access to individual treatment assignments, but will not be involved in subsequent study conduct. The rest of the personnel involved in the conduct of the study, including those at Takeda, Quintiles, and the study sites, will remain blinded to the

individual subject data (including treatment assignments) until unblinding after database lock (Day 210 for Cohort 1 and Day 293 for Cohort 2).

The interim results will be shared with limited personnel at Takeda and will include only aggregate group unblinded reports. Individual results will not be shared with any Takeda personnel or the Quintiles blinded team. The list of team members from the study who are given access to the group results will be documented in an unblinding plan. Statistical Methodology for interim analyses will be the same as for final study analysis, described in previous sections, but may be a subset of the analyses to be performed at the end of the study.

Data listings containing subject-level unblinding information will not be generated for either the Day 57 or Day 140 analyses for Cohort 1 and Cohort 2, respectively.

Complete clinical database subject listings will be provided only at final analysis (ie, Day 210 for Cohort 1 and Day 393 for Cohort 2) after the database is locked

### **7.13 Changes in the Statistical Analysis Plan**

#### *Changes from the Analyses Planned in Protocol Version 3.0, 1 March 2016*

Section 13.1.4 of the Protocol (Version 3.1) referred to exclusion of biologically implausible measurements. Large or implausible outlying values may be identified by medical reviewers during blind data review and queried before database lock. However, no criteria to identify implausible measurements will be defined in this SAP. Due to the age range of the subjects and the multi-regional settings in this trial, a reliable and consistent cut-off for implausible measurements cannot be developed. Hence all values in the database at time of database lock will be included in the analyses.

Section 6.1 in the study protocol indicated that two interim analyses are to be performed after the primary safety and immunogenicity data are available (ie, Day 57 for Cohort 1 and Day 140 for Cohort 2). Cohort 1 consists of 3 age groups enrolled in age step-down fashion. However due to delay in availability of investigational product, enrollment of Group 3 has been delayed. Therefore, the Day 57 interim analysis of Cohort 1 will proceed on schedule but will initially include only age groups 1 and 2. After study enrollment resumes, Day 57 interim analyses of Group 3 will be provided at a later time.

[figure not shown]

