### **9.3.3 Post-vaccination Procedures (Day 1 and Day 29 [Cohort 1] and Day 1, Day 56, and Day 112 [Cohort 2])**

The following post-vaccination procedures will be performed on Day 1 and Day 29 (Cohort 1), and Day 1, Day 56, and Day 112 (Cohort 2).

- Careful training of the subject's LAR on how to measure local AEs and body temperature, how to complete the diary card, and how often to complete the diary card. Training should be directed at the individual(s) who will perform the measurements of local AEs and those who will enter the information into the diary card. This individual may or may not be the subject's LAR, but if a person other than the subject's LAR enters information into the diary card, this person's identity must be documented in the trial file and this person must receive training on the diary card. Training of the subject's LAR on how to measure an injection site reaction should be performed while the subject is under observation after vaccination.

Diary card instructions must include the following:

- The subject's LAR must understand that timely completion of the diary card on a daily basis is a critical component of trial participation. The subject's LAR should also be instructed to write clearly and to complete the diary card in pen. Any corrections to the diary card that are

performed by the person completing the diary card should include a single strikethrough line with a brief explanation for any change and be initialed and dated.

Please note:

Diary cards will be the only source document allowed for remote collection of solicited local and systemic AEs (including body temperature measurements). The following additional rules apply to the documentation of safety information collected by diary card:

- The Diary Card should be reviewed with the subject's LAR.
- No corrections or additions to the diary card will be allowed after it is reviewed with the investigator/designee.
- Any data that is identified as implausible or incorrect, and confirmed by the subject's LAR to be a transcription error should be corrected by the subject's LAR on the diary card (the correction should include a single strikethrough line and should be initialed and dated by the subject's LAR).
- Any blank or illegible fields on the diary card not otherwise corrected as above will be missing in the eCRF.
- The site must enter all readable entries on the diary card into the eCRF.

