### 13.1.4 Safety Analysis

All summaries and analyses of safety data are based on subjects in the Safety Analysis Set. Unless otherwise specified, the safety data will be summarized by formulation arm, (ie. according to the formulation arms, separately for the 1 and 2 (or 2 and 3) dose groups), for each age stratum and overall within each cohort. Further grouping or subgrouping may be investigated as appropriate.

In general, data imputation will not be performed for any missing safety data. The criteria for biologically implausible measurements are defined in the SAP, and any measurements meeting those criteria (eg, body temperature  $>42^{\circ}\text{C}$ ) will be excluded from the summaries and analyses.

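### The protocol says the SAP defines criteria for implausible measurements, but the SAP defines none, so an unresolved impossible temperature can be counted as fever

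*SAP*

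**What the plan says.** Protocol 13.1.4 (Safety Analysis) puts the rule in the SAP: "The criteria for biologically implausible measurements are defined in the SAP". Measurements that meet the criteria "will be excluded from the summaries and analyses". The one example given is body temperature above 42 °C.

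SAP 7.13, under changes from the protocol, withdraws this: "no criteria to identify implausible measurements will be defined in this SAP". Its reason is that, given the age range and the multi-regional setting, "a reliable and consistent cut-off for implausible measurements cannot be developed". Two statements take the place of the exclusion: "Large or implausible outlying values may be identified by medical reviewers during blind data review and queried before database lock" and "Hence all values in the database at time of database lock will be included in the analyses".

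Protocol 9.3.3 governs diary temperatures. The diary card is the only permitted source for readings taken away from the clinic. Every legible entry has to be transcribed to the eCRF. On corrections it says: "No corrections or additions to the diary card will be allowed after it is reviewed with the investigator/designee". The next item in the same list directs the legally authorized representative (LAR) to correct an implausible or wrong entry that he or she confirms was a transcription error.

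SAP 7.11.1 derives fever as yes/no at 38 °C or above for every child and groups temperatures in 0.5-degree bands. It states no upper limit.

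**The concern.** The governing protocol refers to criteria that do not exist. The SAP declares the departure, but Version 4.0 keeps the original rule, so the two documents give different answers for the same reading.

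The SAP's reason does not carry over to temperature. Age and region plausibly complicate a limit for heart rate, height or weight. Yet the same SAP applies a single 38 °C fever threshold from 6 weeks to under 9 years, and the protocol already names an upper limit for temperature.

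The replacement safeguard is optional, and for diary data its reach is uncertain. If an impossible reading is first noticed at blinded data review, the site has already gone through the card with the family. Protocol 9.3.3 does not say whether the transcription-error route is still open then. If it is not, or if the LAR does not confirm an error, the value stays and is analysed.

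Unit slips are foreseeable: the protocol's grading tables accept °C or °F, and SAP 7.1 plans for mixed units. Body temperature is listed as a primary safety endpoint, and Cohort 1 arms have about 15 children per group.

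**Working it through.** The plan gives no figure to reproduce: the trial is descriptive and this point involves no power or alpha.

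**Comparing the texts**

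- Criteria: protocol 13.1.4 says they are in the SAP; SAP 7.13 says there are none.
- Values meeting criteria: excluded under the protocol; included under the SAP.
- Safeguard: a fixed rule in the protocol; review and query that may happen in the SAP.
- Version: the SAP 7.13 heading cites Version 3.0 dated 1 March 2016, and its text cites Version 3.1. Protocol 1.3.1 dates Version 3.0 to 26 March 2015, Version 3.1 to 1 April 2015 and Version 4.0 to 1 March 2016. SAP 7.1 says the plan rests on Version 4.0. The label is wrong, but the substance is unaffected because Version 4.0 keeps the exclusion.

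**Effect of one unresolved reading**

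Inputs: about 15 children per formulation/dose combination per Cohort 1 group and about 45 in Cohort 2 (protocol 6.1); fever at 38 °C or above. Take an afebrile child whose normal 98.6 °F is stored as 98.6 °C. Since 98.6 ≥ 38, the child counts as febrile. The shift in the arm's fever rate is 1/n:

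- n = 15: 1/15 = 6.7 points
- n = 45: 1/45 = 2.2 points
- n = 120 (one Cohort 1 group): 1/120 = 0.8 points
- n = 480 (all of Cohort 1): 1/480 = 0.2 points

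In an arm with no true fever, the exact 95% interval (Clopper-Pearson, which the SAP names for seroresponse rather than fever) changes as follows:

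- 0/15 = 0% (0 to 21.8) becomes 1/15 = 6.7% (0.2 to 31.9)
- 0/45 = 0% (0 to 7.9) becomes 1/45 = 2.2% (0.1 to 11.8)

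Applying the protocol's example limit (42 °C = 42 × 9/5 + 32 = 107.6 °F) returns each arm to the first figure.

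**How often**

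The documents give no error rate, so the rates below are assumptions. Let r be the share of daily diary temperatures that are impossible and still uncorrected at lock, with entries independent. The chance of at least one in an arm of m entries is 1 − (1 − r)^m.

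- Cohort 1 arm: m = 15 × 7 days × 2 injections = 210. For r = 0.01%, 0.1% and 0.5% the chance is 2%, 19% and 65%.
- Cohort 2 arm: m = 45 × 7 × 3 = 945. For the same rates it is 9%, 61% and 99%.

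The range is too wide to support any statement about likelihood. It also overstates the chance of a false fever, because some impossible readings are low and some belong to truly febrile children.

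**The conversion sentence**

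SAP 7.1 defines a centigrade variable but says a Fahrenheit reading is converted to Fahrenheit. Read literally, 98.6 °F would stay 98.6 and count as fever, with no plausibility screen to catch it. Since SAP 7.1 also says all temperature summaries are in centigrade, this is almost certainly a drafting slip.

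**The case against.** The strongest reply is that the change is declared, explained and given a substitute, and that other safeguards exist. Protocol 12.1 provides logic checks for questionable values, site queries and audit-trailed eCRF corrections, so a keying error against the diary can be fixed before lock. The 30-minute in-clinic temperatures go to the eCRF and are outside the diary bar. A reading as extreme as 98.6 °C is among the easiest to notice. SAP 7.1 lists both the recorded and the centigrade value, so an odd reading remains visible. All of this stands and limits how likely the problem is.

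A reader might infer that the diary bar makes late queries futile, so that impossible values must stay. The documents do not support that. The adjacent transcription-error provision covers exactly such entries, and what is missing is a statement of whether it outlasts the diary review. Nothing supports saying that queries would often fail.

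A reader might also work out that one 98.6 among 15 readings near 37 moves a mean by (98.6 − 37)/15 = 4.1 °C. SAP 7.11.1 names no mean for diary temperature, only fever yes/no and bands. The explicit continuous summary is for vital signs (SAP 7.11.3), which are not diary data. Only the general default in SAP 7.1 could produce a diary mean, so the figure should not be used.

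A ceiling is also a partial remedy. It misses in-range slips (36.9 written as 39.6) and low values: 37 labelled °F becomes (37 − 32) × 5/9 = 2.8 °C and creates no fever. It could also hide a true fever (39.0 written as 93.0). That is a reason to keep an include-all table alongside it.

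**Conclusion.** The contradiction between protocol 13.1.4 and SAP 7.13 is real, and the SAP's reason does not justify it for temperature. Its consequence is conditional: an impossible high temperature can remain in the fever and 0.5-degree summaries when a query does not resolve it. The size is 6.7 points per affected child in an arm of 15 and 2.2 points in an arm of 45. This assumes that the child is otherwise afebrile, that the reading is too high rather than too low, and that it is unresolved at lock. The frequency is unknown. In a descriptive trial this is a minor point, worth correcting because the protocol already supplies the rule and the change is small.

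**What to change.** In SAP 7.11, for temperature only, adopt the protocol's own example: a centigrade value above 42 that is still unresolved at lock is treated as missing in the temperature summaries and in the fever derivation. List each such value, and add a sensitivity table with all values included. Limit the departure declared in SAP 7.13 to the other measurements, and amend protocol 13.1.4 to match.

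In the same revision:

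- Correct the SAP 7.1 sentence so that Fahrenheit readings are converted to centigrade. This must accompany the new rule; otherwise, read literally, a normal Fahrenheit reading would exceed 42 and be set to missing.
- Correct the protocol version cited in SAP 7.13.
- State in protocol 9.3.3 whether an LAR-confirmed transcription error can still be corrected after the diary review.

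The cost is a few sentences, one listing and one table. The downside is small: a true fever recorded as an impossible value would be missing from the main table, though it would appear in the sensitivity table.

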#### *Description of the Amendment 1 changes to the initial Statistical Analysis Plan*

The initial NOR-202 SAP (11 February 2016) has been amended to address changes to the NOR-202 study design effected in Protocol Version 4.0, (Amendment 3) 01 March 2016 [4]. A description of those changes follows. Unless otherwise stated, the reason for each of the changes is to align with Protocol Version 4.0 by updating statistical methodology text to reflect the addition of Group 2a to the study.

**Section 4.4, Figure 4.a**

[figure not shown]
Prior Text:

**Figure 1 Schematic of Trial Design**

Amended Text:

**Figure 4.a Schematic of Trial Design**

\* Recently manufactured clinical trial material lots

Reason for Change:

Reflect the addition of Group 2a to the study.

#### Section 4.4, Figure 4.a description

Prior Text:

A total of 720 healthy subjects will be randomized to the following cohorts, with stratification by country and group:

- Cohort 1, N=360 (Group 1: aged 4 to less than 9 years; Group 2: aged 1 to less than 4 years; Group 3: aged 6 months to less than 1 year [N=120 each]): subjects will be randomized with equal probabilities to 1 of the 8 unique combinations of formulation arms and dose groups (ie, 4 formulation arms and 1 or 2 doses). Each of the combinations will consist of approximately 15 subjects per age group.
- Cohort 2 (Group 4: aged 6 weeks to less than 6 months): 360 subjects will be randomized with equal probabilities to 1 of the 8 unique combinations of formulation arms and dose

CONFIDENTIAL

groups (ie, 4 formulation arms and 2 or 3 doses). Each of the combinations will consist of approximately 45 subjects.

Amended Text:

A total of **840** healthy subjects will be randomized to the following cohorts, with stratification by country and group:

- Cohort 1, N=**480** (Group 1: aged 4 to less than 9 years; Group 2: aged 1 to less than 4 years; **Group 2a: aged 1 to less than 4 years**; Group 3: aged 6 months to less than 1 year [N=120 each]: subjects will be randomized with equal probabilities to 1 of the 8 unique combinations of formulation arms and dose groups (ie, 4 formulation arms and 1 or 2 doses). **The additional 120 children, designated as Group 2a, are being included to evaluate the recently manufactured NoV bivalent VLP vaccine formulations prior to enrolling children in Groups 3 and 4.** Each of the combinations will consist of 15 subjects per group. **Thus Cohort 1 consists of 480 subjects in Groups 1, 2, 2a, and 3 combined.**
- Cohort 2 (Group 4: aged 6 weeks to less than 6 months): 360 subjects will be randomized to receive the recently manufactured NoV bivalent VLP vaccine with equal probabilities to 1 of the 8 unique combinations of formulation arms and dose groups (ie, 4 formulation arms and 2 or 3 doses). Each of the combinations will consist of 45 subjects.

Reason for Change:

Reflect the addition of Group 2a to the study.

**Section 4.4, second paragraph following figure description bullets**

Prior Text:

Subjects 6 months to less than 9 years of age (inclusive, Cohort 1) will receive either 1 or 2 doses by IM injection, at least 28 days apart (Days 1 and 29), in *3 age* groups (Group 1: aged 4 to less than 9 years; Group 2: aged 1 to less than 4 years; Group 3: aged 6 months to less than 1 year). Infants 6 weeks to less than 6 months of age (Group 4/Cohort 2) will receive 2 or 3 doses by IM injection given approximately 56 days apart (Days 1, 56, and 112). Routine child and infant vaccinations will be given on schedule per the national guidelines approximately 28 days apart from the investigational vaccine in each age group.

Amended Text:

Subjects 6 months to less than 9 years of age (inclusive, Cohort 1) will receive either 1 or 2 doses by IM injection, at least 28 days apart (Days 1 and 29), in **4 groups comprising 3 age ranges** (Group 1: aged 4 to less than 9 years; **Group 2 and Group 2a: each group** aged 1 to less than 4 years; **and** Group 3: aged 6 months to less than 1 year). Infants 6 weeks to less than 6 months of age (Group 4/Cohort 2) will receive 2 or 3 doses by IM injection given approximately 56 days apart (Days 1, 56, and 112). Routine child and infant vaccinations will be given on schedule per the national guidelines approximately 28 days apart from the investigational vaccine in each age group.

Reason for Change:

Reflect the addition of Group 2a to the study and make it clear that the additional group (2a) is enrolled in the same age range as group 2.

**Section 4.4, fourth paragraph following figure description bullets**

Prior Text:

Two interim analyses will be performed after the primary safety and immunogenicity data are available (ie, Day 57 for Cohort 1 and Day 140 for Cohort 2, primary analysis time point). The interim analyses will be performed by a separate *group* of unblinded statisticians and programmers at Quintiles who will have access to individual treatment assignments but will *not be involved* in subsequent study conduct.

Amended Text:

Interim analyses will be performed after the primary safety and immunogenicity data are available (ie, Day 57 for Cohort 1 and Day 140 for Cohort 2, primary analysis time point). **The Day 57 IA for Cohort 1 will be provided initially for Groups 1 and 2, who will complete Day 57 substantially earlier than Groups 2a and 3. The Day 57 IA for Groups 2a and 3 combined will be provided at a later time. Thus, the Day 57 IA will be conducted in two parts to be followed by the Day 140 IA in Group 4. All interim analyses will be performed by a separate set of unblinded statisticians and programmers at Quintiles who will have access to individual treatment assignments but will not be otherwise involved in subsequent study conduct.**

Reason for Change:

Update the description of interim analysis strategy to align with the protocol description, amended to accommodate the addition of Group 2a and the delayed enrolment of Group 3.

**Section 4.4, Investigational Vaccine:**

Prior text:

Placebo Control:

Saline will be administered as a single control injection (as the final dose) in order to maintain the trial blind for the 1 dose groups in Groups 1, 2, *and* 3 (Cohort 1) and for the 2 dose group in Group 4 (Cohort 2).

Visit Schedule

Clinical trial visits will be performed on Days 1, 8, 29, 36, 57, and 210 for Cohort 1 and Days 1, 8, 29, 56, 63, 84, 112, 119, 140, and 293 for Cohort 2. Telephone contacts will be performed on Days 3, 32, and 134 for Cohort 1 and Days 3, 59, 115, *and* 260 for Cohort 2.

Revised Text:

Placebo Control:

Saline will be administered as a single control injection (as the final dose) in order to maintain the trial blind for the 1 dose groups in Groups 1, 2, **2a** and 3 (Cohort 1) and for the 2 dose group in Group 4 (Cohort 2).

Visit Schedule

Clinical trial visits will be performed on Days 1, 8, 29, 36, 57, and 210 for Cohort 1 and Days 1, 8, 29, 56, 63, 84, 112, 119, 140, and 293 for Cohort 2. Telephone contacts will be performed on Days 3, 32, and 134 for Cohort 1 and Days 3, 59, 115, **200** and 260 for Cohort 2.

Reason for Change:

Reflect the addition of Group 2a and make a correction to the telephone contact schedule for Cohort 2.

**Section 4.4, Duration of Trial:**

Prior Text:

Subjects will be followed for SAEs for 180 days after the last trial dose. Safety follow-up for other unsolicited AEs, and concomitant medications will be for 28 days following each trial dose.

Amended Text:

**Expected duration of trial participation for each subject is up to 210 days (Cohort 1) and 293 days (Cohort 2).** Subjects will be followed for SAEs for 180 days after the last trial dose. Safety follow-up for other unsolicited AEs, and concomitant medications will be for 28 days following each trial dose.

Reason for Change:

Clarify the total expected study duration for each subject.

